The design of the study is a randomised clinical trial (that will be registered at clinicaltrials.gov). Breast cancer patients will be randomised into two groups (group 1: intervention or group 2: control). The patients will be randomized using the Efron's biased coin design. (Efron, 1971) Patients are stratified by duration of radiation therapy/intervention (3 weeks vs. 5 weeks), type of surgery (mastectomy vs. breast conserving surgery and axillary lymph node dissection vs. sentinel node biopsy), and chemotherapy sequence (none vs. sequential vs. concomitant chemotherapy). Randomisation occurs when the informed consent is signed by the patient. Patients need to be referred as eligible candidates by an MD and can give consent only following an intake conversation, giving all information concerning the trial by going through the informed consent with the patient. This design is shown in figure 2.

[figure not shown]

Figure 2: Design of the study.

8) Medical device

Andullation® technology is a horizontal vibration technique, with stochastically modulated vibrations. Lievens (2007) described Andullation® as “a new vibration therapy introduced for medical application approved by the TÜV Rheinland Belgium N.V. and FDA massage mattress VM9100RM”. The technology is build-in in a massage mattress. Several studies show that vibration (Prisby et al., 2008) and horizontal position (Nepal et al., 2012) in general have a positive influence on relaxation, without side effects. References concerning the technology can be found at <http://www.iaat.eu/science/>

The medical device has a CE-mark in classification Pc IIa, type bf with certificate number Z-18-051-P and identification No. 0633.

Composition and dosing

Group 1 (intervention group): 3 to 5-week Andullation® intervention* (depending on and as long as the duration of the radiation therapy) will be performed, 3 times a week for 20 minutes. Patients wear comfortable clothing. The position of the medical device is adapted to the body contours of the patient for an ergonomic position. The patient is lying in a relaxed position with hands posed next to the body on the lateral side of the mattress.

* <https://www.hhp.be/nl/producten/andumedic-3-professional>

Medical device: Andumedic® 3 Professional

Settings of the medical device: a combination of program 3, 8 and 18 (standardized)

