Group 2 (control group) will follow the same intervention protocol as group 1, but without the application of the Andullation® technology. Environmental parameters will be equal to those of group 1.

Producer/distributor

Producer:

International Association of Andullation® Technology (IAAT) - [name] (president dr. [name]) www.iaat.eu

Official dealer:

Home Health Product bvba (HHP) – [name] (CEO [name]) www.hhp.be

Packaging/storage conditions

Normal packaging, transport and storage conditions.

Known side effects

Up to now, there are no negative side effects reported about 20 minutes of Andullation® technology in literature or clinical experience. The Andullation® application is approved as a medical device by TÜV Rheinland Belgium N.V. and FDA massage mattress VM9100RM.

Pregnancy, epilepsy and a recent orthopaedic implant are contra indications reported by the producer and dealer.

Side effects will be registered during the trial.

9) The subjects:

Number of subjects

At the Department of Radiation Therapy of the UZ Brussel, an average of 8 breast cancer patients starts radiation therapy for about 3 to 5 weeks every week. Taking into account the sample size estimation/calculation, the duration of the project (Chair ‘Andullation Care Research’ of the VUB) and the availability of the medical device(s), we have constructed the inclusion schedule below (table 1).

The schedule is based on a 5-week intervention (and control) over a duration of 14 months to include 118 patients for the two study arms. If patients who have only 3 weeks of intervention are included, even more patients can be included. Therefore, insurance is based on the inclusion of maximum 130 patients, taking into account extra (3-week intervention) patients and a drop-out of 10%.

	M1/M2									start/2M	N = (op M14)
	W1	W2	W3	W4	W5	W6	W7	W8	W9		
1st week intervention	2	2	2	2	2	2	2	2	2	18	118
2nd week intervention		2	2	2	2	2	2	2	2		
3rd week intervention			2	2	2	2	2	2	2		
4th week intervention				2	2	2	2	2	2		
5th week intervention					2	2	2	2	2		
interventions/day	2	4	6	8	10	10	10	10	10		
	M13/M14										
	W53	W54	W55	W56	W57	W58	W59	W60	W61		
1st week intervention	2	2	2	2	2						
2nd week intervention	2	2	2	2	2	2					
3rd week intervention	2	2	2	2	2	2	2				
4th week intervention	2	2	2	2	2	2	2	2			
5th week intervention	2	2	2	2	2	2	2	2	2		
interventions/day	10	10	10	10	10	8	6	4	2		

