Table 1: Inclusion schedule of the study.

Inclusion criteria

- Histological proven breast cancer, following breast cancer surgery
- Starting with adjuvant radiation therapy (with or without concomitant chemotherapy) for 3 to 5 weeks
- Age: older than 18 years
- Medical report (possibly for another hospital) is required with:
diagnosis: tumor type and time of 1st biopsy (if relevant)
proposed therapy (start and end dates of each treatment and treatment type)
- Patients have to be able to perform the intervention (laying supine on the mattress for 30', of which 20' intervention)
- A written informed consent has to be signed in the spoken language of the patient. (French, Dutch or English as well as the questionnaires)

Exclusion criteria

- Severe neurological, orthopaedic or rheumatic disorders of the lower or upper limbs which makes it impossible to lay on the mattress in supine position
- Cardiac disorders

- Early or synchronous malignancy
- Pregnancy or lactation
- Persons suffering from depression or illnesses who influence the mental health or wellbeing

Replacement of subjects

A drop-out of 10% was taken into account in the sample size calculation and inclusion schedule. Since we can prolong the intervention with a few weeks (the Chair is assigned for 24 months), we can have an extra medical device of the distributor during the study, we can include more than two patients a week at the UZ Brussel, because there are on average 8 patients starting radiation therapy every week, ... we will be able to anticipate for a bigger drop out.

Restrictions and prohibitions for the subjects

Provocation of vagal nerve activity minimal 24 hours before intervention will be registered prior to every intervention. The use of medication that influences pain sensation, fluid homeostasis, sleep hygiene and stress will be registered.

10) Procedures:

The measurements will be obtained and results will be analysed at the PR4 building of the Universitair Ziekenhuis Brussel, [name].

	Autonomic nervous system	Stress	Pain	Edema	Sleep	Quality of life
Outcome measure	Primary	Secondary	Secondary	Secondary	Secondary	Secondary
Measurement	Heart rate variability through skin sensor (ANSWatch®)			Volume measurement of the arms (Perometer®) for the evaluation of lymphedema Body composition (bioimpedance) for the evaluation of vascular edema		

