Questionnaire		- Distress Thermometer	- Brief Pain Inventory (BPI) - Numeric Pain Rating Scale (NRS)		- Pittsburgh Sleep Quality Index (PSQI) - Insomnia Severity Index (ISI)	- EORTC QLQ BR23

Measurement moment	Before, during and after each intervention	Baseline After each 3 rd intervention Follow-up	NRS: Before and after each intervention, Follow-up BPI: baseline, after each 3 rd intervention and follow-up	Baseline After 3 weeks After 5 weeks (if radiation lasts 5 weeks) Follow-up	Baseline After 3 weeks After 5 weeks (if radiation lasts 5 weeks) Follow-up	Baseline After 3 weeks After 5 weeks (if radiation lasts 5 weeks) Follow-up
--------------------	--	--	--	--	--	--

Table 2: Procedures of the study.

[figure not shown]

Figure 1: These measurements will be repeated in week 3 and if your radiation therapy has a duration of more than 3 weeks, these measurements will also be repeated in week 5.

Questionnaires

- Distress Thermometer
A questionnaire to evaluate in what extent the patient experiences complaints like distress and anxiety, on a visual thermometer. (Mitchell et al., 2007)

- EORTC QLQ BR23
A questionnaire designed to investigate the quality of life in breast cancer patients. (Michels et al., 2013)
- Brief Pain Inventory
This questionnaire was designed to investigate the extent of pain and the influence of it on quality of life. (Abahussin et al., 2018)
- Pittsburgh Sleep Quality Index (PSQI)
This questionnaire was designed to assess sleep quality, quantity and disturbance. (Beck et al., 2004)
- Insomnia Severity Index (ISI)
This questionnaire was designed to assess the severity, nature and impact of insomnia over the past two to four weeks. (Morin et al., 2011)

Body parameters

- ANSWatch®
A device measuring heart rate through skin sensors. With the information withdrawn, the device calculates heart rate variability. (Sun et al., 2011)
- Perometer®
A device measuring arm contours with the use of infrared light. It is an efficient, safe, painless and reliable method to examine arm volumes. (Adriaenssens et al., 2013)
- Bioimpedance
By using bioimpedance, body composition will be estimated. Patients have to stand on scale and hold on to a handgrip that is connected with the scale. A small current will determine the body composition and especially extracellular fluid. This is a painless and innocuous examination. (Seward et al., 2016)

11) Flowchart

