Inclusion (and intervention) will start from the moment we receive a positive advice of the Medical Ethical Comité and will last for 14 months. The project (VUB Chair) is assigned for 24 months in total. An MD will refer patients as potential candidates for the trial after screening of the inclusion criteria and during the intervention, there will always be at least one MD in the PR4 building. (cfr table 1 and figure 2)

12) Randomisation/blinding:

The patients will be randomized using the Efron's biased coin design. (Efron, 1971) Patients are stratified by duration of radiation therapy (3 weeks vs. 5 weeks), type of surgery (mastectomy vs.

breast conserving surgery and axillary lymph node dissection vs. sentinel node biopsy), and chemotherapy sequence (none vs. sequential vs. concomitant chemotherapy).

Blinding is not possible.

13) Prior and concomitant therapy:

The patients are allowed to use every medication needed for their treatment before, during and after the intervention.

Any medication that has an influence on HRV activity, sleep, stress, edema and pain are reported before intake in the trial and monitored throughout the study.

14) Study analysis:

Sample size calculation

Based on our calculation in G*Power (with a medium effect size of 0.5 and with a power = 0.8), the total sample size is 128.

[figure not shown]

Figure 5: Sample size calculation

Analysis of the samples and statistical analysis

The promotor and researcher of the VUB Chair will analyze the samples and do the statistical analysis.

For all statistical analyses, superiority will be based on a two-sided p-value < .05. All statistical computations use SPSS v. 20.0 (IBM Corporation, Somers, NY, 10589, USA). Descriptive statistics will be used to describe medical and demographic characteristics of the population. Normality and homogeneity for both groups will be calculated. The repeated measures ANOVA design will be used to evaluate the changes over time and between groups. Correlations between outcome measures will be calculated as well.

15) Quality control and quality assurance:

The researcher will be present when the intervention is given to install the patient, to start the intervention and to make sure that everything runs according to plan.

The researcher will also make sure that all settings are properly programmed and placed as indicated in the protocol prior to welcoming the patient. The researcher will use the same checklist before starting each intervention.

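### The repeated measures ANOVA has no stated time points, no rule for combining 3- and 5-week patients and no rule for gaps; a mixed model with a named contrast should replace it

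*Combined protocol and SAP*

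**What the plan says.** Section 14 gives one sentence on comparing the groups: "The repeated measures ANOVA design will be used to evaluate the changes over time and between groups". The software is fixed: "All statistical computations use SPSS v. 20.0". The section names no time points for the ANOVA, no way of pooling durations and no treatment of missing readings.

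The schedule is set elsewhere in the protocol:

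- Section 8: the intervention lasts as long as radiotherapy, 3 to 5 weeks, and "will be performed, 3 times a week for 20 minutes".
- Section 12 (and section 7): "Patients are stratified by duration of radiation therapy (3 weeks vs. 5 weeks", so duration is a design factor.
- Section 10, Table 2: the primary outcome, heart rate variability (HRV), is read "Before, during and after each intervention". Edema, sleep and quality of life are measured at baseline, at week 3, at follow-up, and also "After 5 weeks (if radiation lasts 5 weeks".
- Section 9: the schedule recruits 118 patients, while "insurance is based on the inclusion of maximum 130 patients". On attrition: "A drop-out of 10% was taken into account in the sample size calculation and inclusion schedule".
- Section 12 also states that the trial cannot be blinded.

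Table 2 therefore does list measurement moments for every outcome, including a follow-up for all but HRV. What is missing is any link from those moments to the ANOVA.

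**The concern.** The standard repeated measures ANOVA works on a rectangle: the same time points, all present, for every patient. This trial's data are not rectangular by design, because one stratum has 9 sessions and the other 15. They will not be rectangular in practice either, because the protocol itself expects drop-out. The analyst must decide which points to enter, and that decision fixes who is analysed. As written, the number of patients in the primary test, and its power, depend on a choice that can be made after the data are seen. Under section 14 the analysis is done by the promotor and researcher of an unblinded trial, which is a further reason to settle the choice in advance.

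**Working it through.** **Session counts.** 3 per week × 3 weeks = 9 sessions; 3 × 5 = 15. With three HRV readings per session, that is 27 or 45 readings per patient.

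**The plan's own figure.** A two-sided two-sample t-test with d = 0.5, alpha 0.05, power 0.80 and equal arms needs 63.8, so 64 per arm, or 128. This matches section 14. The 128 is a single-comparison figure, so single-comparison power is used below as the yardstick. It is not the ANOVA's own power.

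**Starting numbers.** 118 × 0.9 = 106.2, one reading of the drop-out text (power 72%). 130 × 0.9 = 117 (power 76%).

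**Choice 1: all 15 sessions entered.** No 3-week patient has sessions 10 to 15, so that stratum is excluded. Its share is not in the documents. Assuming 30, 50 or 70%, 106.2 × (1 − share) leaves 74, 53 or 32 patients (power 57, 43 or 28%).

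**Choice 2: the nine shared sessions as separate levels.** Each 5-week patient loses 6 of 15 sessions (40%). With a missed-session rate m, independent across sessions, the complete share is (1 − m)^9. The documents give no m; 1, 2 and 5% are assumed.

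**Choice 3: two aligned points.** The complete share is (1 − m)^2.

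| | m = 1% | m = 2% | m = 5% |
|---|---|---|---|
| Complete, nine sessions | 91% | 83% | 63% |
| Complete, two points | 98% | 96% | 90% |
| Power from 106 (72%), nine sessions | 68% | 64% | 52% |
| Power from 106, two points | 71% | 71% | 68% |
| Power from 117 (76%), nine sessions | 73% | 69% | 56% |
| Power from 117, two points | 76% | 75% | 72% |

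**Choice 4: weekly means over the three shared weeks.** A patient is incomplete only if all three sessions of a week are missed. The complete share is (1 − m³)³; at m = 5% this is (1 − 0.000125)³ = 99.96%.

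**Check with the ANOVA's own group × time test.** Assume 106.2 patients, within-patient correlation 0.5, sphericity, and an effect rising linearly from 0 to 0.5 SD over nine sessions. The noncentrality is (N/4) × Σ(d_j − mean d)² / residual variance.

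- Nine levels: 26.55 × 0.2344 / 0.5 = 12.4 on 8 df, power 70%. This falls to 65, 60 or 46% for complete cases at m = 1, 2 or 5%.
- Weekly means (0.0625, 0.25, 0.4375): 26.55 × 0.0703 / 0.1667 = 11.2 on 2 df, power 85%, with almost no patients lost to scattered misses.

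The nine-level figures depend on the assumed correlation. At 0.7 they are 92% falling to 89, 86 or 72%.

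**The case against.** The best reply is that section 14 nowhere says that every session enters as its own level. A sensible analyst could use first and last readings, weekly means, or one ANOVA per duration, and none of these excludes a stratum. For edema, sleep and quality of life, Table 2 already offers baseline, week 3 and follow-up, which both durations share. Section 9 also allows a longer recruitment period, an extra device and faster inclusion if drop-out is larger than expected. On this view the plan is only under-specified, and stating the time points and a missing-data rule would be enough.

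Much of this stands. A reader might infer that the planned method necessarily loses a third or more of the patients. The documents do not support that: the 63% applies to one unstated version of the ANOVA at an assumed 5% miss rate. A reader might also infer a biased result. Gaps at random cost power only. Bias needs missingness that differs by arm, which is possible in an unblinded trial but which nothing in the documents shows.

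The reply does not remove the point. The plan adopts none of these alternatives. First versus last treats session 9 and session 15 as the same point and discards everything between. Weekly means over the shared weeks ignore weeks 4 and 5. Separate ANOVAs split the sample. Under each of them, a patient who drops out before an entered time point is still excluded. Recruiting more patients restores numbers but sets no rule for incomplete ones.

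**Conclusion.** The point holds as a gap in the plan with a cheap and better alternative, and it should be fixed before the data are analysed. The only planned between-group analysis needs identical, complete time points. The schedule gives 9 or 15 sessions, and the plan does not say which points enter, how durations combine, or what happens to gaps and drop-outs.

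The cost ranges from negligible (weekly means) through small (two points: 72% to 71, 71 or 68%) to large (nine levels: 72% to 68, 64 or 52%). It is larger still if all 15 sessions enter and the 3-week stratum is excluded. These figures rest on assumed independent misses of 1, 2 and 5%, equal arms, d = 0.5, and 106 patients remaining after drop-out. Starting from 106 also carries in the separate gap between the 118 scheduled and the 128 calculated, which this point does not address; the losses from 117 are similar.

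**What to change.** In section 14, replace the ANOVA with a linear mixed model (SPSS MIXED, within the stated package):

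- **Patients and data:** all randomised patients in their allocated group, with every available reading of one HRV index and one within-session reading. The sponsor names both in advance.
- **Terms:** the HRV value before session 1 as covariate (not also as an outcome), the stratification factors, group, session, group × session, and duration terms. State the within-patient covariance structure. If group is allowed to interact with duration, fix the weights for averaging over durations in advance. If a course between 3 and 5 weeks can occur, say how it is classed.
- **Primary contrast:** the group difference at session 9 (end of week 3), the last session that both durations share.
- **Secondary contrast:** week 5, in 5-week patients only. Never impute sessions that a patient was not scheduled to have.
- **Missing data:** state the missing-at-random assumption. Add one simple sensitivity analysis for scheduled but missed readings, such as imputing them with pre-stated shifts in the intervention arm.
- **Secondary outcomes:** the same approach at their Table 2 visits, including follow-up.

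The cost is one paragraph of text and slightly more analysis work, with no new data or software. The downside is that the primary contrast does not cover weeks 4 and 5. The model also cannot recover readings after drop-out.
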